## **B. Randomized Evaluation of COVID-19 Therapy (RECOVERY): Efficacy of dexamethasone**

The RECOVERY trial, which first reported preliminary results on June 22, 2020, was an open-label, 1:2 randomized controlled trial of 6,425 patients randomized to either 6 mg of DEX daily for 10 days (n = 2,104) or usual care (n = 4,321). Overall, 22.9% of patients assigned to the DEX group died within 28 days of randomization vs. 25.7% of the control arm (rate ratio [RR] of 0.83, 95% CI [0.75, 0.93]). The difference in survival between the two groups varied noticeably when stratified by baseline COVID-19 severity level. While the incidence of death was lower in the DEX group, compared to the usual care group, among patients receiving IMV (RR: 0.64, 95% CI [0.51, 0.81]) and among those receiving supplemental O2 therapy but not IMV (RR: 0.82, 95% CI [0.72, 0.94]), there was no discernable difference among patients who were not receiving any supplemental O2 (RR: 1.19, 95% CI [0.91 to 1.55]) [*RECOVERY 2020*].

The effectiveness of DEX in preventing death among moderate to severe COVID-19 patients has not yet been confirmed or established in routine care, yet DEX utilization has substantially increased in the US since June 2020 [*Action 2021*]. Thus, to evaluate the effectiveness of DEX in preventing death under routine use in a timely manner, we sought to conduct an observational cohort study using US-based real-world data (RWD).

[figure not shown]
In one of the explorations conducted prior to the finalization of this protocol [see *Appendix A.2. Exploration 2*], we compared the distribution of key patient characteristics between a version of our hospitalized US-based RWD study cohort to those reported for the hospitalized UK-based patients randomized in the RECOVERY trial. The RECOVERY trial was a large, pragmatic randomized trial that simplified the data collection process in an effort to minimize the already heavy burden of the pandemic on frontline workers. Exploration of baseline clinical differences between the real-world study and trial populations was therefore limited by the degree of available information for the trial patients. However, among the available RECOVERY trial data, we identified important clinical and demographic differences in the trial population versus this study's populations at baseline.

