Given the periodic data updates during the *Exploratory Phase*, explorations were carried out on earlier cuts of the data. Therefore, although the cohort design remained relatively consistent across explorations, the cohort samples used for each exploration differed from each other, and from the final cohort that will be used for the diagnostic and inferential phases of the analysis [See *IV. Data Source*].

For the *Diagnostic Phase*, we developed a checklist of diagnostic criteria [see *section VI.B, Table 4*] that must be satisfactorily completed prior to beginning the implementation of the *Inferential Phase*. As such, the relationship between the treatment and outcome of interest will not be described or evaluated in the analytic dataset until we reach consensus that the diagnostic criteria are satisfied. Upon each data update, the Diagnostic results will be presented to the FDA RCA team until there is consensus that we have satisfied the necessary criteria to progress to the *Inferential Phase* [see *section VI.C*].

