### III. RESEARCH AIM AND OBJECTIVES

As part of the RCA with the FDA, this study informs the overall project to establish a system for rapid-cycle evaluation, using best practice scientific and operational methods, as applied to relevant and meaningful clinical questions. In this study, we seek to assess the effectiveness of DEX to reduce the risk of inpatient mortality within 28 days among US patients hospitalized with COVID-19 diagnosis or SARS-CoV-2 infection, overall and stratified by COVID-19 severity subgroups [defined according to the presence of encounters indicating supplemental oxygen or ventilation; see *section V.D* for additional subgroup detail], using the HealthVerity database.

The principles outlined by Hernan et al. emphasize the importance of explicitly emulating a hypothetical target trial when planning a RWD analysis to yield RWE [Hernan, Robins 2016; Hernan, Sauer 2016]. Although we reference the UK RECOVERY trial as a basis for comparison [RECOVERY 2020], we sought to emulate a hypothetical target trial with varied design elements, and research questions tailored for US practice and US patients. In a sensitivity analysis, we further sought to replicate the RECOVERY trial design elements (to the extent possible) [see *section VII. Sensitivity Analyses, SA8*].

Specifically, among US patients hospitalized with COVID-19 diagnosis or SARS-CoV-2 infection without prior use of any corticosteroid of interest (CSI; DEX, methylprednisolone, prednisone, hydrocortisone) estimate the hazard ratio and corresponding 95% confidence interval for the risk of inpatient mortality within 28 days after treatment initiation, comparing *new use of DEX* with:

- *non-users of corticosteroids (Primary objective I; DEX+ vs. CSI-)*, to evaluate the potential benefit of DEX above ‘standard of care’ inpatient treatment for COVID-19, where ‘standard of care’ excludes all CSIs (DEX, MPRED, PRED, HC).
- *non-users of DEX (Secondary objective I; DEX+ vs. DEX-)*, to evaluate the potential benefit of DEX above ‘standard of care’ inpatient treatment for COVID-19, where ‘standard of care’ excludes DEX but may include those newly treated with a non-DEX CSI (MPRED, PRED, HC). This comparison is most similar to the RECOVERY trial that compared DEX to ‘standard of care’ [RECOVERY 2020].

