**VII. SENSITIVITY ANALYSES**

The following eight sensitivity analyses (SA1-SA8) in *Table 5* below were determined *a priori*. Additional sensitivity analyses may be considered *post hoc* upon review of preliminary results with the FDA RCA team. Unless otherwise specified, all sensitivity analyses will be applied in response to the primary objective but not the secondary objectives.

*Table 5: Summary of all sensitivity analyses planned a priori*

Category	Brief Description	Detail / Purpose
Inclusion/exclusion criteria (more specific)	SA1: Restrict study population to hospitalizations occurring after release of initial RECOVERY findings*	
Detail: Restrict cohort entry to on or after June 16, 2020, given the release of the RECOVERY results in early June 2020.
 
Purpose: Evaluate whether there is (qualitative) heterogeneity of the HR (which may be due to treatment pattern changes) after the substantial increase in DEX use in the US.

	SA2: Restrict study population to patients with immediate treatment initiation*	
Detail: Restrict DEX treatment index to DEX initiation on, or within 1d after, admission date.
 
Purpose: Evaluate whether there is (qualitative) heterogeneity of the HR (which may be due to covariate differences in patients treated earlier vs. later in the hospital stay) when restricting to DEX use upon admission, noting that the 1 day after admission was added to account for patients who may be admitted late in the evening who do not initiate treatment until the next morning.

Inclusion/exclusion criteria (more sensitive)	SA3: Broaden population to include patients with less frequent medical encounters*	
Detail: Lengthen baseline window to lookback 365 days to allow for better capture of covariates among patients who do not have as frequent medical encounters (office visit or otherwise). Evaluate whether covariate status using 183 day versus 365 day lookback is differential by treatment.
 
Purpose: Evaluate whether HR is robust within a broader cohort that may include people with less healthcare utilization (patients without a healthcare encounter within 183 days that do have one within 365 days prior to admission) prior to hospitalization for COVID-19. Determine if the lookback period impacts the distribution of baseline characteristics.

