Inclusion/exclusion criteria related to RECOVERY	SA8: One comprehensive sensitivity analysis that attempts to more closely resemble RECOVERY population	
Detail:
 
 
1. Remove new user washout
 
2. Exclude patients aged 80 years or older
 
3. Exclude patients with systemic fungal infections
 
 
Purpose: To more closely align with RECOVERY design and baseline population
 
 
1. RECOVERY included any use of DEX.
 
2. Our study population has half the number of patients 80+ as RECOVERY due to under-report of older patients in our commercial data source, and these patients may therefore be selectively different.
 
3. RECOVERY trial excluded patients contraindicated “in the opinion of the attending clinician.” Systemic fungal infection is the only contraindication listed in the package insert for DEX, so excluding these patients is an attempt to satisfy this criterion.
 

\* Alternative versions of the study diagrams for these sensitivity analyses are illustrated in Appendix B.

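### SA8 is presented as the RECOVERY-like analysis, but dropping patients aged 80+ makes the cohort less like RECOVERY on age, and by default SA8 omits the DEX- comparator that the plan itself calls closest to RECOVERY

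*Protocol*

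**What the plan says.** Section III says the study emulates its own target trial and keeps RECOVERY as a reference. It then points to SA8 as the exception: "we further sought to replicate the RECOVERY trial design elements (to the extent possible". Table 5 states the purpose of SA8 as "To more closely align with RECOVERY design and baseline population" and lists three changes: removing the new-user washout, "Exclude patients aged 80 years or older", and excluding systemic fungal infection. For the age step it argues that the data source under-reports older patients, and that "these patients may therefore be selectively different".

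Table 5 names no comparator for SA8. The opening of Section VII therefore governs: "Unless otherwise specified, all sensitivity analyses will be applied in response to the primary objective but not the secondary objectives". The primary objective is DEX+ vs CSI-. Section III says of Secondary objective I (DEX+ vs DEX-): "This comparison is most similar to the RECOVERY trial that compared DEX to" standard of care. Tables A.1 and A.2 in Appendix A.2, which set the study beside RECOVERY, also use patients without DEX as the referent.

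The RECOVERY results quoted in Section II.B cover all ages: "Overall, 22.9% of patients assigned to the DEX group died within 28 days of randomization vs. 25.7% of the control arm", with a rate ratio of 0.83 overall and 0.64, 0.82 and 1.19 by respiratory support. No result for patients under 80 is quoted or planned.

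**The concern.** Appendix A.2 reports that RECOVERY patients were older than the study cohort. Removing the oldest patients from the younger of two populations cannot bring its overall age mix closer to the older one. The reason given for the exclusion concerns how well the data source represents patients aged 80+. That can justify an under-80 analysis, but it does not make an under-80 cohort resemble a trial in which more than one patient in five was 80 or older.

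The comparator has a similar problem. The analysis meant to mirror RECOVERY is run, by default, only against the referent that the plan does not regard as the RECOVERY-like one. Section III expects a stronger effect against CSI- than against DEX-, on the assumption that all the corticosteroids of interest are protective.

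What is at stake is interpretation. SA8 is the only analysis presented as resembling RECOVERY, so its hazard ratio is the natural one to set beside the trial's. Agreement or disagreement could then reflect the age cut or the referent. Secondary objective I supplies a DEX- result, but without SA8's criteria.

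**Working it through.** **Inputs (Appendix A.2, Table A.2).**

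| | Study DEX+ | Study DEX- | RECOVERY DEX | RECOVERY usual care |
|---|---|---|---|---|
| N | 1840 | 1840 | 2104 | 4321 |
| Under 70 | 1193 | 1184 | 1141 | 2504 |
| 70 to 79 | 359 | 360 | 469 | 859 |
| 80+ | 288 | 296 | 494 | 958 |
| Mean age | 62.48 | 62.71 | 66.9 | 65.8 |

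The table's percentages reproduce from these counts. The Table 5 statement that the study has half as many 80+ patients as RECOVERY does not: the pooled count ratio is 584/1452 = 0.40, the DEX+ count ratio 288/494 = 0.58, and the pooled share ratio 15.9/22.6 = 0.70. The argument does not rest on that statement.

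**Share aged 80+, arms pooled.** Study (288 + 296)/3680 = 15.9%. RECOVERY (494 + 958)/6425 = 22.6%. The gap is 6.7 points. After the exclusion the study share is 0%, so the gap is 22.6 points.

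**Share under 70, arms pooled.**
- Before: study (1193 + 1184)/3680 = 64.6%; RECOVERY (1141 + 2504)/6425 = 56.7%; gap 7.9 points.
- After, against all-age RECOVERY: study 2377/(3680 - 584) = 2377/3096 = 76.8%; gap 20.0 points.
- After, if RECOVERY were cut at 80 too: 3645/(6425 - 1452) = 3645/4973 = 73.3%; gap 3.5 points.

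**Mean age.** The removed patients average at least 80, so (N × mean - n80 × 80)/(N - n80) is an upper bound on the mean that remains.
- DEX+: (62.48 × 1840 - 288 × 80)/1552 = 59.23. The gap to RECOVERY goes from 66.9 - 62.48 = 4.4 to at least 7.7 years.
- Referent: (62.71 × 1840 - 296 × 80)/1544 = 59.40. The gap goes from 65.8 - 62.71 = 3.1 to at least 6.4 years.

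**Mean age, both sources under 80.** The documents do not give the mean age of the 80+ patients, so a common value is assumed and varied.

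| Assumed mean age of 80+ | Study DEX+ under 80 | RECOVERY DEX under 80 | Gap (years) |
|---|---|---|---|
| 82 | 58.86 | 62.27 | 3.4 |
| 85 | 58.30 | 61.35 | 3.0 |
| 88 | 57.74 | 60.43 | 2.7 |

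The exclusion narrows the original 4.4-year gap only when it is applied to both sources.

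**By severity (Table A.3, arms pooled).** The 80+ share, study against RECOVERY, is 16.5% vs 35.0% with no oxygen and 15.5% vs 23.1% on oxygen, so the exclusion widens the gap in both. On invasive ventilation it is 8/124 = 6.5% vs 16/1007 = 1.6%. There the exclusion helps: the under-70 share goes from 78.2% to 97/116 = 83.6% against 83.2%.

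**Comparator.** No arithmetic applies. The Section VII default and SA8's silence give DEX+ vs CSI- only. Section III names DEX+ vs DEX- as closest to RECOVERY and says SA8 replicates the trial's design as far as possible. The DEX- cohort is already to be built for Secondary objective I, so adding it is possible.

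**The case against.** The strongest defence of the age step is that it limits the analysis to an age range the data source captures adequately and never claims that the age mix will match. Read that way, and with RECOVERY also cut at 80, the two populations do come closer (3.5 points on the under-70 share instead of 7.9). This stands as a case for an under-80 analysis. It does not rescue the stated purpose, because the protocol names no under-80 RECOVERY comparison and quotes only all-age results. Appendix A.2 promises to weigh differences from the trial in interpretation, but that does not change what SA8 estimates.

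The reversal in the invasive ventilation stratum is real. It covers 62 patients per arm, 3.4% of that cohort, and the point made here concerns the overall cohort.

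Table A.2 is an early DEX+/DEX- cut, while SA8 as written would run on a DEX+/CSI- cohort, and Section II.C warns that "the cohort samples used for each exploration differed from each other, and from the final cohort" to be analysed. The magnitudes will therefore change. The direction is more robust: removing patients aged 80+ lowers the mean of any cohort whose mean is below 80, so it widens the gap whenever the cohort is already younger than RECOVERY.

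On the comparator, holding the primary referent fixed is ordinary practice, and Table 5 files SA8 under eligibility criteria. CSI- should indeed stay, so that SA8 can be compared with the primary analysis. That is no reason to leave out DEX-, since both Section III and the Table 5 purpose refer to RECOVERY's design as well as its population.

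**Conclusion.** Both parts hold. In the overall cohort, the 80+ exclusion moves SA8 away from all-age RECOVERY on age: 22.6 instead of 6.7 points on the 80+ share, 20.0 instead of 7.9 points on the under-70 share, and a DEX+ mean-age gap of at least 7.7 instead of 4.4 years. These sizes rest on the exploratory cohort of Table A.2. The direction requires only that the final cohort is also younger than RECOVERY. By default SA8 also omits DEX-, the referent the plan considers most RECOVERY-like.

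The consequence is confined to comparing SA8 with RECOVERY. SA8 gates no other analysis and the primary estimate does not change. The size of any effect on the hazard ratio cannot be derived from the protocol.

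**What to change.** In Table 5:
- Remove the 80+ exclusion from SA8.
- List the under-80 restriction as its own sensitivity analysis, justified by data capture and not described as alignment with RECOVERY's all-age population.
- State that SA8 is run for DEX+ vs DEX- as well as DEX+ vs CSI-. The first gives the comparison with RECOVERY; the second keeps the change from the primary analysis interpretable.

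The cost is a change of wording and one or two extra runs on a comparator that is already planned. The one drawback is that 80+ patients who may be unrepresentative stay in SA8; the separate under-80 result shows how much they matter. The change should be made before the Inferential Phase, when treatment effects are first examined.

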## VIII. POTENTIAL LIMITATIONS

### A. Addressed in Design and Analyses

The following limitations have been addressed via study design or analyses, but will still be taken into consideration when interpreting and disseminating the findings from the implementation of this protocol:

- **Difficulty determining COVID-19 severity for the modified WHO categorization:** Oxygen supplementation is critical to the mWHO COVID-19 severity categorization (IMV, O2/NIV, no O2) upon admission and upon treatment initiation. Although it seems IMV is generally well captured via procedural claims data alone, it is unclear if oxygen support is fully captured via procedural claims. We have developed algorithms to determine IMV or O2/NIV support based on the presence of relevant procedures or diagnoses, but determination of no O2 will rely on the absence of recorded procedures or diagnoses for IMV or O2/NIV, which may increase the potential for misclassification in the no O2 group. Furthermore, given the lack of day-level diagnostic information (i.e., only admitting and discharge diagnoses are available), there is potential for under-reporting of severity on days during the hospital stay. Lastly, reporting of ARDS used to define IMV might not have been as well captured early in the pandemic, so there is increased potential for misclassification among patients hospitalized earlier in the study period. The inclusion of ECMO in the IMV definition may minimize the potential for under-report of ARDS since ECMO has been given as a short-term rescue therapy in patients with ARDS. In SA1, we restrict cohort entry to on or after June 16, 2020, given the release of the RECOVERY results in early June 2020 [see *section VII. Sensitivity Analyses, SA1*]. Through this analysis, we will be able to see how ARDS is reported among patients after the early months to better understand this concern. Further, SA7 allows us to evaluate the impact of the shift from lower to higher COVID-19 severity on the effect of DEX+ on 28-day mortality using an algorithm that relies on procedural encounters only for defining O2/NIV and IMV [see *section VII. Sensitivity Analyses, SA7*].
- **COVID-19 diagnosis:** The unique ICD-10 code for COVID-19 diagnosis (U07.1: COVID-19, virus identified) was created by the World Health Organization (WHO) in April 2020. Prior to the widespread use of the new code, other respiratory-related codes were used for billing purposes. We chose to delay the start of our cohort selection to April when the code was available. There is a possibility that early on, some facilities were not yet using the new code. However, given our findings from exploration 1 [see *Appendix A.1. Exploration 1*], concerns about the specificity of the ICD-10 codes other than the designated U07.1 code, we agreed to proceed with the definition of confirmed COVID-19 via diagnosis of U07.1 or positive/presumptive positive SARS-CoV-2 diagnostic laboratory test result.
- **Unstructured laboratory encounter data:** In addition to using the unique diagnosis code for COVID-19 (ICD-10: U07.1), we will include patients without a diagnosis claim if they have laboratory results identifying positive or presumed positive SARS-CoV-2 diagnostic test via nucleic acid amplification test (NAAT). The laboratory data has unstructured free-text for test type and results, which present a challenge. Although we anticipate that we will not be able to categorize all COVID-19 laboratory results, we rely on an algorithm developed by the data vendor to discern the majority of test types and results.

- **Open claims:** Data from open claims can be captured within days of a healthcare encounter to provide near-real-time data. However, the composition and completeness may be less stable for the most recent calendar dates. Based on our findings from exploration 5, we have truncated cohort entry to remove the last 60 days, which should minimize this concern [see *Appendix A.5 Exploration 5*].
- **Lack of enrollment information in open claims to determine denominator of patients at risk with the same potential to contribute baseline data:** Without beneficiary enrollment information like that included with closed claims data, use of “open” datasets limits the ability to clearly determine when a patient is observable or “at risk.” However, we are confident that our cohort will include all patients hospitalized available in the data and will additionally require the presence of any encounter during the 183-day baseline period for inclusion as a proxy for enrollment and extend this period to 365 days in a sensitivity analysis.
- **Unstructured inpatient medication data:** Unlike outpatient pharmacy data, inpatient medication data in the HealthVerity data is largely captured via vendor charge code fields (e.g., ‘DEXAMETHASONE 4 MG OR TABS’) in addition to medical procedural claims such as HCPCS for medication administration (e.g., J1095 - INJECTION, DEXAMETHASONE ACETATE, PER 8 MG) that have non-standardized free-text descriptions rather than standardized fields (e.g., NDC codes). Therefore, text search strings will be used to query the data when procedure codes are not available. For this reason, it is possible that some of the patients included using our primary definition for systemic DEX may have non-systematic use that was not excluded due to a lack of indication in the search string. However, we assume this to be rare. Our team has developed a series of search string algorithms to minimize the potential for error and will incorporate additional manual review for key measures.
- **Potential for residual confounding:** Although best practices will be applied to control for confounding, the potential for residual confounding still exists in observational cohort analyses. We will apply RSS to match on time-related biases, which are assumed to be strong given the evolving healthcare landscape of the COVID-19 pandemic that will include other matching factors of importance (i.e., time since admission, age, sex, and comorbidity score). Furthermore, we will use PS matching on top of RSS matching and will not conduct inferential comparative analyses until we have satisfied the balancing criteria specified in the diagnostic checklist. Finally, a number of *a priori* specified sensitivity analyses will evaluate the robustness of our findings. If warranted, post hoc sensitivity analyses may also be conducted to evaluate the potential impact of unmeasured confounding. Although we recognize that factors causing residual confounding may manifest after index, this study does not account for changes in disease severity and other COVID-19 treatment received after index date to avoid additional potential bias that may be induced by conditioning on mediating variables in the causal pathway, or on colliders.
- **Completeness of tobacco/smoking covariate:** Smoking/tobacco use will be defined according to the presence of the indicator for current or past user in the electronic health record (EHR), a diagnosis indicating use or abuse of tobacco, or presence of a procedural consultation or medication dispensed for cessation. The addition of EHR data makes this definition more complete than algorithms based on claims alone, but misclassification via under-reporting of smoking behavior is likely.

